11.2.8.2. Sample Size

[REDACTED]

- [REDACTED]
- [REDACTED]
- [REDACTED]
- [REDACTED]
- [REDACTED]

[REDACTED]

11.2.8.3. Statistical Methods

All subjects with a RELIANCE 4-FRONT lead that undergo an induction test within 30 days of implant will contribute to the analysis of this endpoint. If multiple tests or multiple configurations are tested in the 30 day post-implant period, the last induction test in its final configuration will be used in the analysis. A one-sided exact binomial test will be performed on all subjects with induction data (regardless of lead fixation or coil type) and the resulting lower exact (Clopper-Pearson) confidence interval will be calculated, using an alpha equal to █%. If the lower one-sided 95% confidence limit for the conversion rate is greater than 93%, the null hypothesis will be rejected.

11.2.9. RELIANCE 4-FRONT Ancillary Analyses

11.2.9.1. RELIANCE 4-FRONT Ancillary Safety Objective

The RELIANCE 4-FRONT Ancillary Safety Objective will be used to prospectively determine the chronic five year complication-free rate of the RELIANCE 4-FRONT RV lead. The overall sample size required for this endpoint is greater than the sample size of this NAVIGATE X4 study. The remaining leads will be enrolled under a separate post-market approval study protocol. Data from this study and data from the post-approval study protocol will be pooled for purposes of analysis.

11.2.9.2. Additional Analyses for RELIANCE 4-FRONT

To assess the long term performance of electrical measurements, pacing threshold, sensed amplitude, and pacing impedance at 24 months will be summarized using descriptive statistics. Spontaneous VT/VF events will also be summarized with descriptive statistics.

11.3. General Statistical Methods

All sample size calculations were performed and all statistical analyses will be done with SAS version 9.1 or higher.

11.3.1. Study Success Criteria

The study success will be determined █ for ACUITY X4 and RELIANCE 4-FRONT. Each study will be considered successful if all primary endpoints specific to that lead are passed

11.3.2. Analysis Sets

The following analysis sets will be used for each endpoint. Note that for all analyses, the final lead implanted or attempted from the initial procedure will contribute to the analysis.

Endpoint	Analysis Sets
ACUITY X4 Primary Safety Endpoint	All subjects implanted or attempted with ACUITY X4
ACUITY X4 Primary Effectiveness Endpoint 1	All ACUITY X4 leads with measurements taken at the three-month follow-up visit

December 17, 2013
FINAL

Boston Scientific
NAVIGATE X4 Study Protocol
90874504 Version AB
Page 62 of 101

Endpoint	Analysis Sets
ACUITY X4 Primary Effectiveness Endpoint 1	All ACUITY X4 [REDACTED] leads with measurements taken at the three-month follow-up visit
ACUITY X4 Secondary Effectiveness Endpoints 1 & 2	All ACUITY X4 leads with measurements taken at the three-month follow-up visit
ACUITY X4 Ancillary Safety Objective	Analysis will not be performed at the time of report submission since 60-month data from this study will be pooled with data from an ACUITY X4 Post-Market Approval Study
RELIANCE 4-FRONT Primary Safety Endpoint 1	All subjects implanted or attempted with RELIANCE 4-FRONT
RELIANCE 4-FRONT Primary Safety Endpoint 2	All subjects implanted with RELIANCE 4-FRONT that have been followed for at least [REDACTED] days post-implant
RELIANCE 4-FRONT Secondary Safety Endpoint	All subjects implanted with RELIANCE 4-FRONT that undergo an induction test within 30 days of implant will contribute to the analysis of this endpoint
RELIANCE 4-FRONT Ancillary Safety Objective	Analysis will not be performed at the time of report submission since 60-month data from this study will be pooled with data from a RELIANCE 4-FRONT Post-Market Approval Study
RELIANCE 4-FRONT Primary Effectiveness Endpoint	All RELIANCE 4-FRONT leads with measurements taken at three month follow-up visit
RELIANCE 4-FRONT Secondary Effectiveness Endpoints 1 & 2	All RELIANCE 4-FRONT leads with measurements taken at three month follow-up visit
RELIANCE 4-FRONT Secondary Effectiveness Endpoint 3:	All subjects implanted with RELIANCE 4-FRONT that undergo an induction test within 30 days of implant will contribute to the analysis of this endpoint

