10.5.3. Right Ventricular Lead Selection

10.5.3.1. ██████████ NAVIGATE X4

Any commercially available Boston Scientific cardioversion/defibrillation lead may be used ██████████ NAVIGATE X4. BSC recommends the use of RELIANCE 4-FRONT. Documentation of RV lead choice will be collected ██████████ NAVIGATE X4.

10.5.3.2. ██████████ NAVIGATE X4

RELIANCE 4-FRONT is required in ██████████ NAVIGATE X4. If RELIANCE 4-FRONT is attempted, but not successfully implanted, the subject may still be a part of the study ██████████ ██████████ and a commercially available RV lead is acceptable. Boston Scientific RV leads are required.

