11.2.8.1. Hypotheses

The percent of successful VT/VF conversions with a RELIANCE 4-FRONT lead will be compared to a performance goal of 93%, [REDACTED]. The null hypothesis will therefore be rejected in favor of the alternative if the upper confidence limit of the observed percent of successful conversions is greater than 93%. The conversion will be considered successful if the device converts the subject without the need for external defibrillation. [REDACTED]

[REDACTED]

H₀: Percent of successful conversion ≤ 93%

H_a: Percent of successful conversion > 93%

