2.3 Index Procedure

As stated in the protocol, the final lead implanted or attempted in a chamber from the initial procedure will contribute to the analysis of all applicable endpoints. This criterion will apply separately for ACUITY X4 and RELIANCE 4-FRONT.

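### The analysis-set rows for the two RELIANCE 4-FRONT induction endpoints conflict with the plan's general lead rule; applied as written, they would drop a lead that failed to convert and was exchanged for another lead family

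*Protocol*

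**What the plan says.** Protocol 11.2.8.1 frames the question as lead performance: "The percent of successful VT/VF conversions with a RELIANCE 4-FRONT lead will be" compared with a goal of 93%. Protocol 11.2.8.3 takes as its population "All subjects with a RELIANCE 4-FRONT lead that undergo an induction test within 30 days of" implant, scores the last induction test in its final configuration, and rejects the null if the one-sided 95% Clopper-Pearson lower limit is above 93%.

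The table in Protocol 11.3.2 defines the set for this endpoint as "All subjects implanted with RELIANCE 4-FRONT that undergo an induction test within 30 days of implant", and does the same for the Secondary Safety Endpoint (detection time). The Primary Safety Endpoint 1 row of that table reads "All subjects implanted or attempted with RELIANCE 4-FRONT".

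Above the table stands a general rule: "Note that for all analyses, the final lead implanted or attempted from the initial procedure will contribute to the analysis". SAP 2.3 repeats it, saying that "the final lead implanted or attempted in a chamber from the initial procedure will contribute to the analysis of all applicable endpoints", and adds: "This criterion will apply separately for ACUITY X4 and RELIANCE 4-FRONT".

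Protocol 10.5.3 provides for a lead that does not stay in: "If RELIANCE 4-FRONT is attempted, but not successfully implanted, the subject may still be a part of the study", with a commercially available right ventricular lead in its place.

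**The concern.** Induction testing may be done at implant, so the result can be known while the lead can still be exchanged. Suppose a RELIANCE 4-FRONT lead fails to convert, is taken out, and a right ventricular lead of another family is put in during the same procedure. The RELIANCE 4-FRONT lead was then attempted and not implanted. The 11.3.2 row read alone leaves the subject out; the note above the table and SAP 2.3 read alone keep the lead in. No section says how a lead removed after a failed induction is scored.

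Under the row reading, membership of the set depends on the outcome being tested. A conversion failure is a reason to remove the lead and a success is not, so this route takes out failures only. The observed rate would be biased upward against the 93% goal, and the exact binomial test would no longer hold its stated error rate.

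**Working it through.** **1. The passages side by side, for a final RELIANCE 4-FRONT lead that failed induction**

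| Text | Lead left in place | Exchanged for another RELIANCE 4-FRONT | Exchanged in the same procedure for a non-RELIANCE lead |
|---|---|---|---|
| 11.3.2 row, read alone | in, counted as a failure | subject in; the last test, on the new lead, counts | **out** |
| 11.3.2 note and SAP 2.3 | in, counted as a failure | the final RELIANCE 4-FRONT lead counts | **in**, but its score is not stated |

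The conflict is confined to the last column.

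**2. Inputs for the size**

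- Goal 93% and decision rule (one-sided 95% Clopper-Pearson lower limit above 93%): Protocol 11.2.8.1 and 11.2.8.3. Section 11.2.8.1 also contains a sentence that refers to the upper limit. The lower limit is used here because it matches the stated hypotheses.
- Number of subjects tested: blacked out in 11.2.8.2, and testing is optional under 10.5.12. Assumed n = 100, 200 and 300.
- Number of failures dropped by exchange: not given. Assumed d = 0, 1 and 2.

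Because the sample size text is blacked out, there is no planned figure to reproduce.

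**3. Largest number of failures that still passes**

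With x successes in n, the lower limit is the 5th percentile of Beta(x, n − x + 1).

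| n | Maximum failures, c | Lower limit at c | Lower limit at c + 1 | Lower limit at c + 1 failures with one subject dropped |
|---|---|---|---|---|
| 100 | 2 | 93.8% | 92.4% | 93.8% (2 failures in 99) |
| 200 | 7 | 93.5% | 92.9% | 93.5% (7 in 199) |
| 300 | 13 | 93.2% | 92.8% | 93.2% (13 in 299) |

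At the boundary, dropping one subject turns a fail into a pass.

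**4. Pass probability when the true conversion rate is exactly 93%**

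With d failures dropped, find c for n − d subjects. It is unchanged at 2, 7 and 13 for d = 1 and d = 2. The trial then passes if the true number of failures is at most c + d, so the pass probability is P[Binomial(n, 0.07) ≤ c + d].

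| n | d = 0 | d = 1 | d = 2 |
|---|---|---|---|
| 100 | P(X ≤ 2) = 2.6% | P(X ≤ 3) = 7.4% | P(X ≤ 4) = 16.3% |
| 200 | P(X ≤ 7) = 2.7% | P(X ≤ 8) = 5.6% | P(X ≤ 9) = 10.1% |
| 300 | P(X ≤ 13) = 3.8% | P(X ≤ 14) = 6.5% | P(X ≤ 15) = 10.3% |

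Against the nominal 5%, one dropped failure is an excess of 0.6 points (5.6 − 5.0) to 2.4 points (7.4 − 5.0). The rise over the d = 0 column is larger because the exact test is conservative when nothing is dropped.

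**The case against.** The strongest reply is that the plan already includes the lead. The note in 11.3.2 covers all analyses, and SAP 2.3 covers all applicable endpoints, separately for each study lead. Protocol 9.3 classes a subject as an implant subject if implanted and/or tested with a study lead, and sends such subjects into all analyses. Section 11.2.8.3 speaks of subjects with the lead, without the narrower term. This reply stands to a large extent. A reader might infer from the row that exclusion is the settled rule; the documents do not support that. What they show is a specific row and a general note that disagree, with no order of precedence. Even if the note prevails, the removed lead's score is left unstated.

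Three further limits also stand.

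- A reader might see a clean contrast between safety rows and the rest. That is not so: the Primary Safety Endpoint 2 row and the detection-time row, itself a safety row, also use the narrower term.
- A reader might carry the bias over to detection time, since its row has the same wording. A lead that fails to convert need not have detected slowly, so no bias in the mean is shown.
- A reader might think any exchange loses the subject. With another RELIANCE 4-FRONT lead, the subject stays in the denominator and the last-test rule decides the score.

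Finally, the documents describe no exchange prompted by a failed induction. Section 10.5.12 mentions only changes of vector, polarity or lead position. The route is permitted by 10.5.3 but is not shown to be common.

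**Conclusion.** The point holds as an unresolved conflict of wording with an identifiable consequence. If the 11.3.2 row is applied as written, a conversion failure followed by a same-procedure exchange to another lead family is removed because of its outcome, in the direction that favours success.

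The size is conditional on the row prevailing, on at least one such exchange occurring, and on the assumed range of n. Since one subject can decide the result at the boundary, rarity lowers the chance of harm but does not make the rule safe.

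The severity is minor. Under Protocol 11.3.1, success for each lead rests on its primary endpoints, and this is a secondary test.

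**What to change.** Make two wording changes.

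1. In the table of Protocol 11.3.2, put the rows for Secondary Effectiveness Endpoint 3 and the Secondary Safety Endpoint on an implanted-or-attempted basis, so that they agree with the note above the table and with SAP 2.3.
2. Add a scoring rule to Protocol 11.2.8.3: where a subject's final RELIANCE 4-FRONT lead is removed after an unsuccessful induction and replaced by a lead of another family, that lead's last induction result counts as a conversion failure, and inductions on the replacement lead are not used.

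Exchanges to another RELIANCE 4-FRONT lead stay under the existing last-test, final-configuration rule. This is a scoring rule for the analysis only and changes nothing about how subjects are tested or treated.

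The cost is an edit to the protocol, with matching SAP text if wanted, and recording the induction result for the removed lead. The reported conversion rate may be slightly lower.

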11.3.3. Control of Systematic Error/Bias

Selection of subjects for enrollment will be made from the Investigator’s usual patient load. All subjects meeting the eligibility criteria and having signed the ICF will be eligible for enrollment in the study.

11.3.4. Control of Type-I Error

Control of type-I Error will be handled separately for ACUITY X4 and RELIANCE 4-FRONT.

ACUITY X4

Each primary endpoint can be tested at the significance level specified in Section 11.1 ([REDACTED]).

For each lead, due to the requirement that each applicable endpoint must be passed, each applicable endpoint can be tested at the specified significance level while still maintaining the overall type-I error level at no greater than [REDACTED]%. This follows the methodology of the Intersection-Union Test (IUT).

If all primary endpoints are passed, then a gating approach will be employed to test the following secondary endpoints in this order:

December 17, 2013
FINAL

Boston Scientific
NAVIGATE X4 Study Protocol
90874504 Version AB
Page 63 of 101

11.4.2. Pooling Analyses

11.4.2.1. RELIANCE 4-FRONT Pooling of Cohorts

It is expected that results will not differ [REDACTED] for any endpoint, with the exception of Secondary Effectiveness Endpoint 2. In order to confirm the poolability for each endpoint, a pooling analysis will be performed. Specifically, a likelihood ratio test from a regression model will be conducted. The type of regression model used for each of the following endpoints is as follows:

- Primary Safety Endpoint 1 (CFR from Implant to 3 Months): Logistic Regression
- Primary Safety Endpoint 2 (CFR from 3 to 24 Months): Logistic Regression
- Secondary Safety Endpoint (Detection of VT/VF): Linear Regression
- Primary Effectiveness Endpoint (Pacing Threshold at 3 Months): Linear Regression
- Secondary Effectiveness Endpoint 1 (Sensed Amplitude at 3 Months): Linear Regression
- Secondary Effectiveness Endpoint 3 (VT/VF Shock Conversion): Logistic Regression

The regression model will include additional baseline covariates to attempt to adjust for any imbalances between baseline data. The following baseline covariates will be considered: age, gender, etiology, CRT-D indication, LVEF, NYHA classification, medications, arrhythmia history, associated diseases/risk factors, height, weight and geography. [REDACTED]

[REDACTED]

[REDACTED]

[REDACTED]

[REDACTED]

[REDACTED]

[REDACTED]

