11.2.2.1. Hypotheses

The following hypotheses will be used to evaluate RELIANCE 4-FRONT Primary Safety Endpoint 2 [REDACTED]:

H₀: The lead-related complication-free rate from 3 to 24 months ≤ 94%

H_a: The lead-related complication-free rate from 3 to 24 months > 94%

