11.2.3. Statistical Methods

Data from all RELIANCE 4-FRONT leads that have been followed for at least [REDACTED] days post-implant at the time of endpoint analysis will be eligible for inclusion in the endpoint analysis. All RELIANCE 4-FRONT leads [REDACTED] will be pooled for this analysis.

December 17, 2013
FINAL

Boston Scientific
NAVIGATE X4 Study Protocol
90874504 Version AB
Page 56 of 101

The lead-related complication-free rate from [redacted] days through [redacted] days post-implant will be calculated using Kaplan-Meier methodology. The 95% one-sided lower pointwise confidence limit of the complication-free rate will be calculated via log-log methodology for all eligible subjects and compared to the performance goal of 94%. If the lower confidence limit exceeds 94%, the null hypothesis will be rejected.

Each lead’s exact follow-up time in the period between [redacted] days post-implant will be included in the analysis due to the rate being calculated via Kaplan-Meier methodology. The leads that reach [redacted] of follow-up but fail to reach [redacted] of follow-up (without experiencing an endpoint event in the period prior to their end of follow-up) will be censored at the time of their end of follow-up in the period. Because non-informative censoring cannot be assumed for these leads, a tipping point analysis will be performed to determine the potential effects these censored leads could have on the results if full information on each lead was present. The tipping point analysis will assign each lead that was censored between the [redacted] [redacted] post-implant as either having or not having an endpoint event. The tipping point will be determined by the point at which the endpoint results turn from passing (null hypothesis) to failing (null hypothesis rejected). An exact binomial test will be performed for the tipping point analysis.

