11.4.2.4. Pooling of investigational centers

Center-to-center heterogeneity will be assessed for each endpoint by performing random effects regression analyses. Centers with less than five enrollments will be combined to form “supercenters”. Small centers will be combined until the newly created supercenter has five enrollments, and then a new supercenter will be created. The following regression models for each of the following endpoints will be used:

ACUITY X4

- Primary Safety Endpoint (CFR from Implant to 6 Months): Random Effects Logistic Regression
- Primary Effectiveness Endpoint 1 (Pacing Threshold at 3 Months, programmed): Random Effects Logistic Regression
- Primary Effectiveness Endpoint 2 (Pacing Threshold at 3 Months, best proximal): Random Effects Logistic Regression
- Secondary Effectiveness Endpoint 1 (Sensed Amplitude at 3 Months): Random Effects Linear Regression
- Secondary Effectiveness Endpoint 2 (Pacing Impedance at 3 Months): Random Effects Linear Regression

RELIANCE 4-FRONT

- Primary Safety Endpoint 1 (CFR from Implant to 3 Months): Random Effects Logistic Regression

December 17, 2013
FINAL

Boston Scientific
NAVIGATE X4 Study Protocol
90874504 Version AB
Page 66 of 101

- Primary Safety Endpoint 2 (CFR from 3 to 24 Months): Random Effects Logistic Regression
- Secondary Safety Endpoint (Detection of VT/VF): Random Effects Linear Regression
- Primary Effectiveness Endpoint (Pacing Threshold at 3 Months): Random Effects Linear Regression
- Secondary Effectiveness Endpoint 1 (Sensed Amplitude at 3 Months): Random Effects Linear Regression
- Secondary Effectiveness Endpoint 2 (Pacing Impedance at 3 Months): Random Effects Linear Regression
- Secondary Effectiveness Endpoint 3 (VT/VF Shock Conversion): Random Effects Logistic Regression

Investigational center will be added into the model as a random effect. Centers will be deemed to be heterogeneous if the variance of the random center effect is found to significantly differ from zero. A significance level of ■% will be used for each test. If it determined that the center random effect is significant for an endpoint, then the results from the random effects model for that endpoint will be presented. Regardless of the results of the random effects model, results by investigational center will be presented for each endpoint.

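### RELIANCE Primary Safety Endpoint 2 (3–24 months) is estimated by Kaplan-Meier, but its pooling, centre and subgroup models are logistic with no visible rule for censored leads; supporting analyses only.

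*Protocol*

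**What the plan says.** Protocol section 11.2.3 defines the endpoint analysis. A lead that enters the window but stops before its end without an event "will be censored at the time of their end of follow-up in the period". The decision rests on the one-sided 95% log-log Kaplan-Meier limit: "If the lower confidence limit exceeds 94%, the null hypothesis will be rejected". The section then adds: "Because non-informative censoring cannot be assumed for these leads, a tipping point analysis will be performed".

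The supporting models for the same endpoint are:

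- **Cohort pooling (11.4.2.1):** "Primary Safety Endpoint 2 (CFR from 3 to 24 Months): Logistic Regression", tested by likelihood ratio with baseline covariates. Redacted blocks follow the covariate list.
- **Centres (11.4.2.4):** "Primary Safety Endpoint 2 (CFR from 3 to 24 Months): Random Effects Logistic Regression". If the centre effect is significant, "then the results from the random effects model for that endpoint will be presented". Small centres are merged: "Centers with less than five enrollments will be combined to form" supercentres. Only the significance level is blacked out in this section.
- **Subgroups (11.4.3):** univariate models, stated to be the same as in 11.4.2.1, hence logistic.
- **Multivariate (11.4.4):** a regression model whose type is not named. Logistic is an inference there.

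SAP section 1 refers back to the protocol for the analyses, and SAP section 2 says nothing on censored leads.

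**The concern.** Kaplan-Meier uses a censored lead up to its last day. A standard logistic model cannot: the lead must be coded event-free, dropped, or weighted. The first coding understates the event proportion and the second overstates it, so the fitted result depends on a choice that is not visible.

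Two outputs are exposed. If centres prove heterogeneous, the random-effects logistic result is presented for a primary safety endpoint and need not agree with the Kaplan-Meier CFR. And a subgroup test may report a difference in complications that is partly a difference in length of follow-up. Death, withdrawal and loss over 21 months could differ by age, NYHA class or LVEF, though the documents do not quantify this.

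**Working it through.** **Plan's own figure.** The only related figure is the synopsis statement of at least 80% power for every endpoint. It cannot be reproduced, because the expected CFR, attrition and sample size for this endpoint are redacted, and it does not bear on this point.

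**Inputs.** From the documents: the 94% goal (11.2.2.1); 1876 leads in the RELIANCE dataset (SAP 2.2); a lower enrolment bound of 1542 and up to 125 centres (7.1). Assumed: CFR 97% as an alternative; n = 1000 as a low case, because RELIANCE was optional in Phase 1 (8.2); 5–30% censored; nominal 5%, because the plan's level is redacted.

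**Step 1: what a yes/no model sees.** Scale the window to [0,1], with constant event and independent censoring hazards a = −ln(CFR) and m = −ln(1−c), where c is the share censored.

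- P(event seen) = a/(a+m) × (1 − e^−(a+m))
- Completers = e^−(a+m)
- Coded event-free: CFR = 1 − P(event seen)
- Dropped: CFR = completers / (completers + P(event seen))

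Example with CFR 94% and c = 20%: a = 0.0619 and m = 0.2231, so completers = 0.752 and P(event seen) = 0.0538. Event-free coding gives 94.62%; dropping gives 0.752/0.8058 = 93.32%.

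Shift in CFR, in percentage points:

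| Censored | 94%, event-free | 94%, dropped | 97%, event-free | 97%, dropped |
|---|---|---|---|---|
| 5% | +0.15 | −0.15 | +0.08 | −0.08 |
| 10% | +0.30 | −0.31 | +0.15 | −0.16 |
| 20% | +0.62 | −0.68 | +0.31 | −0.35 |
| 30% | +0.94 | −1.14 | +0.47 | −0.59 |

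**Step 2: size of the univariate subgroup test.** Two equal groups with the same true CFR, logistic likelihood ratio test, 200,000 simulated studies per case, n = 1000 to 1876, both codings:

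| Censored, group 1 vs 2 | Rejects a true null |
|---|---|
| 10% vs 10%, 20% vs 20% | 5.0–5.3% |
| 5% vs 10% | 5.1–5.4% |
| 10% vs 20% | 5.4–6.1% |
| 10% vs 30% | 6.3–9.9% |

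The higher values belong to CFR 94% and larger n. Allowing for variation between runs, I take about 5.4–6.5% for 10% vs 20% and about 6–10% for 10% vs 30%. With front-loaded events (Weibull shape 0.5), 10% vs 30% spans 5.7–13.7%. A Cox likelihood ratio test under the same independent censoring (constant hazard) rejects 4.8–5.4%.

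**Step 3: power.** With a true hazard ratio of 2, CFR 97% in the reference group, a 70:30 split, n = 1876 and 10% vs 30% censored, power at nominal 5% is 60% (event-free), 87% (dropped) and 76% for an exposure-based test. The coding alone moves the answer.

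**Step 4: dependent censoring.** Let a shared gamma frailty (variance 1, assumed) act on both events and censoring, with 10% vs 30% censored and n = 1876. The ranges below reflect how the rates are calibrated, marginally or given frailty 1.

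| Test | CFR 94% | CFR 97% |
|---|---|---|
| Log-rank (Cox score test) | 7.0–8.5% | 6.1–6.8% |
| Logistic, dropped | 4.7–5.1% | 4.8–5.4% |
| Logistic, event-free | 15.3–21.9% | 10.5–13.2% |

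**Step 5: shorter windows.** At an assumed 3–5% loss, the Step 1 formulas give shifts of 0.10–0.17 points for the 3-month RELIANCE endpoint (CFR 93%) and 0.18–0.37 for the 6-month ACUITY endpoint (CFR 85–87%).

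**The case against.** The strongest case against runs as follows.

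- **Redaction.** Blacked-out text follows the covariate list in 11.4.2.1, where a coding rule would naturally sit. A rule there would carry to 11.4.3 by reference and could be meant for 11.4.2.4, a sibling section. This stands: a reader might infer that the plan has no rule, but the documents support only that none is visible. Because 11.4.2.4 has no cross-reference to 11.4.2.1, the scope of any hidden rule would still need confirming.
- **No decision changes.** A reader might infer that the pass/fail result is at risk, or that the centre model replaces it. Neither follows. Section 11.2.3 decides on the Kaplan-Meier limit, and 11.4.2.4 says only that the random-effects result is presented. Results by centre and by subgroup are promised in any case.
- **Small effect.** The synopsis places the analysis after all subjects with the RELIANCE lead complete the 24-month visit, so administrative censoring of NAVIGATE leads should be small. Life expectancy under twelve months, transplant listing and chronic dialysis are exclusions. This stands, although follow-up of the leads that SAP 2.2 takes from separate studies is not shown.
- **Limited quantification.** The simulations cover a two-group test without covariates. Adjustment in 11.4.2.1 could absorb part of an attrition difference. This stands.
- **Cox is not a cure.** It assumes non-informative censoring, which 11.2.3 says cannot be assumed. Step 4 bears this out: dropping censored leads held its size better than the log-rank test there. It is therefore wrong to infer that Cox beats every logistic coding.

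**Conclusion.** The mismatch between a censored Kaplan-Meier endpoint and logistic supporting models is in the visible text, and correcting it is a cheap improvement, not a necessity. It affects the pooling, centre and subgroup analyses of one endpoint; the test against 94% is untouched.

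For the univariate subgroup test the inflation is nil with equal censoring, roughly 0.4–1.5 points for 10% vs 20%, and roughly 1–5 points for 10% vs 30%, at nominal 5%. These figures rest on assumed censoring shares, constant hazards, independent censoring and n = 1000 to 1876. The effect on the centre random-effects model and the covariate-adjusted pooling model is unknown. Confidence is medium, because a rule may exist in redacted text.

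**What to change.** For RELIANCE Primary Safety Endpoint 2:

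- Use Cox regression with a likelihood ratio test in 11.4.2.1 and 11.4.3, and in 11.4.4 if a regression is fitted there. Use Cox with a centre frailty in 11.4.2.4. Keep the origin, horizon and censoring of the Kaplan-Meier analysis.
- Report Kaplan-Meier CFRs by subgroup and centre beside the models, since hazard ratios and frailty models do not estimate the marginal CFR.
- Keep the tipping-point analysis, and add a sensitivity analysis of the supporting models for informative censoring.
- If logistic is kept, state or confirm one coding or weighting rule for censored leads (for example inverse-probability-of-censoring weights), apply it in 11.4.2.1, 11.4.2.4, 11.4.3 and 11.4.4, and show the alternative coding.

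The same change for the 3-month RELIANCE and 6-month ACUITY safety endpoints is optional, for consistency.

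The cost is SAP wording and a different model call on data already held. Downsides are a proportional-hazards check and sparse events per centre: 3–6% of 1876 leads is 56–113 events, or about 0.5–0.9 per centre if all leads came from 125 centres, before small centres are merged. The random-effects logistic model has the same sparsity.
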